8.1.2. Serious Adverse Events (SAEs)

A serious adverse event (SAE) is an untoward medical occurrence or effect associated with the use of a study drug at any dose, regardless of whether it is considered to be related to the study drug, which results in one of the following:

- Death (ie, all deaths on treatment or within 6 weeks after last study drug administration), including deaths due to disease progression. Any death occurring later than 6 weeks following the last dose need not be reported as a serious adverse event unless it is a result of an event that started within the period covered by the on-study definition. The reported adverse event should be the event that caused the death. In addition, any adverse event

resulting in death that occurs subsequent to the adverse event-reporting period and that the investigator assesses as possibly related to the study drug should also be reported as serious.

- **Life-threatening adverse event.** This is an event that, in the view of either the investigator or the sponsor, places the patient at immediate risk of death. It does not include an event that, had it occurred in a more severe form, hypothetically might have caused death.
- **Inpatient hospitalization or prolongation of existing hospitalization** (eg. excluding hospitalizations for administration of the study drug, procedures required by the study protocol, or DBMD-related diagnostic procedures; other planned hospitalizations; or hospitalizations related only to progression of disease). Treatments in the emergency room for procedures such as hydration that do not require admitting the patient to the hospital and observational durations in the emergency room for less than 24 hours are not considered serious.
- **Persistent or significant disability or incapacity or substantial disruption of the ability to conduct normal life functions, not related to dystrophinopathy.**
- **Any other medically important event that the investigator or the sponsor judges to be serious or which is defined as serious by the regulatory agency in the local country.** Medical judgment should be exercised in deciding whether a reaction is serious in other situations. Important medical events that do not result in death, are not immediately life-threatening, and do not require hospitalization may be considered serious when, based on appropriate medical judgment, they may jeopardize the patient and may require medical or surgical intervention to prevent any of the outcomes listed above. Examples of such medical events include allergic bronchospasm requiring intensive treatment administration in an emergency room or at home, newly diagnosed malignancy, or blood dyscrasias, or convulsions that do not result in inpatient hospitalization, or the development of drug dependency or drug abuse.

An event need not be reported as a SAE if it exclusively represents a relapse or an expected change or progression of the baseline dystrophinopathy. This type of event need only to be reported as an adverse event.

Note that any SAEs occurring after the end of the patient's participation in the study should be reported to the sponsor if the investigator becomes aware of them.

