Most patients with dystrophinopathy are characterized as having DMD; these patients experience onset of symptoms during early childhood [Ciafaloni 2009]. A small subset (~10%) of boys is classified as having BMD, a phenotypically milder form of dystrophinopathy that is associated with later manifestation of symptoms [Emery 1991]. DMD usually first manifests in boys ~3 to 7 years of age when they are noted to develop lordosis, a waddling gait, and the Gowers' sign (a characteristically abnormal method of rising from a supine to a standing position) [Brooke 1989, McDonald 1995, Boland 1996, Worton 2001]. Inexorable progressive weakness is seen, particularly in the proximal musculature. Ambulation becomes increasingly abnormal. By the age of 8 years, most boys have difficulty rising from the floor and ascending stairs and they often fall while walking. Boys with the disease spend less time walking and walk more slowly than healthy boys [McDonald 2005a] and are significantly less active than normal boys of similar age [McDonald 2002, McDonald 2005b]. By 10 to 14 years of age, most are wheelchair-bound. In ambulatory DMD boys, the most frequent cardiac abnormality is sinus tachycardia and heart rate variability, occurring from childhood and persisting throughout life [Finsterer 2003, Gulati 2005]. Pulmonary function is usually normal before 10 years of age and is well

maintained into adolescence in boys receiving corticosteroids [Mendell 1989, Griggs 1991, Phillips 2001, Tangsrud 2001, Biggar 2001, Biggar 2006]. Later in adolescence, cardiac and diaphragmatic muscles become progressively weaker and patients require treatment for cardiac insufficiency and ventilatory support. Patients usually die of cardiac or pulmonary failure by 15 to 22 years of age [Brooke 1989, McDonald 1995, Simonds 1998, Worton 2001, Eagle 2002].

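### Protocol 8.1.2 makes life-threatening events serious without exception, then exempts any event that is only disease progression, so a life-threatening progression event can be classed either way

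*Protocol*

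**What the plan says.** Protocol 8.1.2 defines an SAE by outcome. The first criterion is "Death (ie, all deaths on treatment or within 6 weeks after last study drug administration), including deaths due to disease progression". The second is an event that "places the patient at immediate risk of death"; it says nothing about progression. The hospitalization criterion leaves out planned or study-related stays "or hospitalizations related only to progression of disease", and the disability criterion is confined to disruption of "normal life functions, not related to dystrophinopathy". A last criterion covers other medically important events.

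After the criteria comes a general sentence: "An event need not be reported as a SAE if it exclusively represents a relapse or an expected change or progression of the baseline dystrophinopathy". It is followed by the instruction "This type of event need only to be reported as an adverse event".

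Protocol 8.1.1 adds, with a cross-reference to 8.1.2, that an inpatient stay caused by any adverse event is to be reported as an SAE. It states no exclusion for progression.

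The SAP does not define an SAE. SAP 5.7.1 tabulates serious and non-serious treatment-emergent adverse events (TEAEs) as they were classified.

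**The concern.** The criteria handle disease progression one at a time: included for death, excluded for hospitalization and disability, not mentioned for life-threatening and medically important events. The general sentence then cuts across all of them. It applies to any event, whatever its outcome, and the text does not say which rule prevails.

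Events of this kind are foreseeable. Protocol 2.1 describes the natural course thus: "Patients usually die of cardiac or pulmonary failure by 15 to 22 years of age". An investigator could reasonably regard a cardiac or respiratory crisis as expected progression. That link is an inference from the disease description; the documents name no such event as exempt. The study is open-label with no concurrent control arm, so the judgement cannot be checked against an untreated group.

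At stake are the speed with which the sponsor hears of such an event and the comparability of SAE counts between sites that read 8.1.2 differently. Long-term safety is the primary objective, and Protocol 10.4.3 singles out SAEs for special attention.

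**Working it through.** No figure in the plan can be reproduced here. The check is a comparison of the text, followed by tracing what the serious label controls.

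**Step 1. Each criterion in 8.1.2 against the general exemption**

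| Criterion | Its own rule on progression | Effect of the general exemption |
|---|---|---|
| Death | Expressly included | Direct conflict |
| Life-threatening | None | Literally permits non-serious classification |
| Hospitalization | Progression-only stays excluded | Adds little, but 8.1.1 conflicts with the exclusion |
| Disability | Dystrophinopathy-related disability excluded | Adds little |
| Medically important | None | Literally permits non-serious classification |

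Because two criteria already carry their own exclusion, the general sentence does most of its work on the other three. For death there is a specific clause to set against it. For life-threatening events there is none.

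**Step 2. The hospitalization sentence in 8.1.1**

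Progression is itself to be recorded as an adverse event under 8.1.2. Read literally, 8.1.1 therefore makes a progression-only admission an SAE, while 8.1.2 excludes it. The cross-reference to 8.1.2 suggests that 8.1.1 was meant to be subordinate, but it does not say so.

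**Step 3. What depends on the serious label**

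- Reporting (Protocol 8.9, Table 7): serious events go to the sponsor's safety department within 24 hours; non-serious events follow the routine case report form process.
- Follow-up (Protocol 8.7): the extra report within one calendar week applies to SAEs that are fatal or life-threatening, so it too depends on the classification.
- Tables (SAP 5.7.1): serious and non-serious TEAEs are shown separately.

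**Step 4. What does not depend on it (SAP 5.7.1)**

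- All TEAEs by system organ class, preferred term and severity grade.
- All TEAEs of grade 3 or higher.
- The count and listing of deaths.

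**Step 5. Size**

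The documents give no rate of life-threatening progression events. Only the weight of one reclassified patient can be shown. Protocol 10.1 gives about 220 patients as the upper bound. If a patient's only serious event is exempted, the percentage with at least one SAE falls by 1/220 = 0.45 percentage points. For illustration, 5 such patients give 5/220 = 2.3 points and 10 give 10/220 = 4.5 points. With fewer enrolled, each patient weighs more. These are sensitivities, not estimates.

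**The case against.** The strongest reply concerns deaths. The death clause addresses progression by name, whereas the exemption is general, permissive and silent on death. The ordinary construction is that the specific clause governs. This stands. A reader might infer that fatal events can drop out of the safety results, but the documents do not support that: SAP 5.7.1 tabulates and lists deaths separately.

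Second, the exemption has an evident everyday purpose. SAP 5.8.4 and 8.3 take loss of ambulation from disease progression recorded as an adverse event, which is the sort of expected decline the sentence seems written for, and the word exclusively narrows it. This explains the intention but does not limit the wording.

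Third, the investigator is not the only judge. Under 8.1.2 the sponsor's view also counts for the life-threatening and medically important criteria. Protocol 9 requires consultation with the medical monitor when a patient worsens substantially, with cardiac examples, and the data monitoring committee in Protocol 11.2 includes a cardiologist. These are real checks, but none settles which rule applies, and a site that files an event as non-serious need not notify the safety department within 24 hours.

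Fourth, there is no separate SAE endpoint. The primary endpoint in Protocol 3.3 is the profile of adverse events and laboratory abnormalities, and exempted events stay in it. This stands, and it limits the analytic loss to the serious/non-serious split.

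Fifth, Protocol 14.3 reports few SAEs and no deaths in Study 007, which had 174 boys (Protocol 2.2.3) treated for 48 weeks. That is relevant background, but it gives no rate of life-threatening events over 144 weeks.

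**Conclusion.** The inconsistency is real and lies within one section. Its practical reach is narrower than the wording might suggest. The main exposure is a life-threatening event judged to be solely progression: the criteria make it serious, the exemption allows it to be non-serious, and nothing in either document decides between them. What can be lost is rapid reporting, the one-week follow-up and a place in the serious-TEAE tables. The event itself is not lost, because it remains in the adverse event, severity and grade 3 or higher tables.

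A reader might go further and infer that most serious cardiac or respiratory events would be hidden, or that the primary endpoint fails. The documents support neither: they give no event rate, and the primary endpoint takes in all adverse events.

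The conclusion rests on two assumptions: that some sites would apply the exemption as written, and that some life-threatening events would be attributed wholly to progression. The number affected cannot be estimated. The point still merits correction, because a stated rule, and not merely a missing detail, permits the non-serious label.

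**What to change.** Reconcile the criteria and the exemption in Protocol 8.1.2, together with the hospitalization sentence in 8.1.1. One added sentence would do: the progression exemption does not cover an event that meets the death or life-threatening criterion.

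SAP 5.2 records that the sponsor has decided to discontinue the study, so new wording alone would do little for data already collected. Before database lock, query adverse events recorded as progression, cardiac or respiratory that are grade 4 or 5 or had a fatal outcome, and align their seriousness with the clarified rule. If seriousness cannot be aligned, add a table to SAP 5.7.1 showing serious TEAEs with and without those attributed to progression. If alignment succeeds, that table is optional.

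The cost is one sentence, a short data query and at most one extra table. The downside is a few more SAE forms and a slightly higher SAE count.

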8.1.3. Unexpected Adverse Events

Unexpected adverse events are defined as those events that were not previously reported with study drug as referenced in the most current investigator brochure, or that are symptomatically and pathophysiologically related to a known toxicity but differ because of greater severity or specificity. For example, under this definition, hepatic necrosis would be unexpected (by virtue of greater severity) if the investigator brochure only referred to elevated hepatic enzymes or hepatitis. Similarly, cerebral thromboembolism and cerebral vasculitis would be unexpected (by virtue of greater specificity) if the investigator brochure only listed cerebral vascular accidents. "Unexpected," as used in this definition, also refers to an adverse event that is mentioned in the most current investigator brochure as occurring with the class of drugs or as anticipated from the pharmacological properties of the study drug, but is not specifically mentioned as occurring with the medicinal product.

For the purposes of considering expectedness, the ataluren investigator brochure provides a summary of the safety profile of ataluren based on available clinical information (also referred to as the reference safety information).

8.2. Eliciting Adverse Event Information

The investigator is to report all directly observed adverse events and all adverse events spontaneously reported by the study patient or parent/guardian in case of a child. In addition, each study patient will be questioned about adverse events at each scheduled clinic visit after study drug administration or during any telephone contact with the patient or parent/guardian in case of a child. The type of question asked should be open-ended, eg, “*How has your child been feeling?*” or a similar type of query.

8.3. Adverse Event Recording

All adverse events (both serious and nonserious) that occur in patients during the adverse event reporting period must be recorded, whether or not the event is considered drug related. In addition, any known untoward event that occurs subsequent to the adverse event reporting period that the investigator assesses as possibly related to the investigational drug/product should also be recorded as an adverse event.

All adverse events are to be recorded in the source documents and on the CRF using concise medical terminology; whenever possible terms contained in Medical Dictionary for Regulatory Activities (MedDRA) should be employed. In addition, the following information should be recorded:

- Indication of whether the event is serious or nonserious (see [Section 8.1.2](#))
- Relationship to study drug (see [Section 8.4](#))
- Severity of the event (see [Section 8.5](#))
- Onset date
- Resolution date, or date of death
- Action taken
- Outcome of the event

Classification of the event as serious or nonserious determines the reporting procedures to be followed.

8.4. Describing Adverse Event Relationship to Study Drug

Based on the considerations outlined in [Table 5](#), the investigator should provide an assessment of the relationship of the adverse event to the study drug, ie, whether there is a reasonable possibility that the study drug caused the adverse event.

Table 5. Relationship of Study Drug to Adverse Event

Relationship	Description
Probable	A clinical event in which a relationship to the study drug seems probable because of such factors as consistency with known effects of the drug; a clear temporal association with the use of the drug; improvement upon withdrawal of the drug; recurrence upon rechallenge with the drug; lack of alternative explanations for the event.
Possible	A clinical event occurring coincident with administration of the study drug and which may or may not be explained by concurrent disease or other drugs or chemicals. Information on drug withdrawal or rechallenge may be lacking.
Unlikely	A clinical event with a temporal relationship to the study drug exposure that does not preclude causality but for which there is a clear alternate cause that is more likely to have caused the adverse event than study drug. Such alternatives include a concomitantly administered drug, the patient's disease state, other medical conditions, or environmental factors.
Unrelated	A clinical event, for which a relationship to the study drug seems improbable because of factors such as inconsistency with known effects of the study drug, lack of a temporal association with study drug administration, lack of association of the event with study drug withdrawal or rechallenge, and/or presence of alternative explanations for the event. Alternative explanations might include a known relationship of the adverse event to a concomitant drug, medical history of a similar event, the patient's disease state, other medical conditions, or environmental factors.

8.5. Grading of Severity of Adverse Events

The severity of adverse events will be graded using the CTCAE, Version 3.0 (refer to Study Manual or to <http://ctep.cancer.gov/forms/CTCAEv3.pdf>). For each episode, the highest severity grade attained should be reported

If a CTCAE criterion does not exist, the investigator should use the grade or adjectives: Grade 1 (mild), Grade 2 (moderate), Grade 3 (severe), Grade 4 (life-threatening), or Grade 5 (fatal) to describe the maximum intensity of the adverse event. For purposes of consistency with the CTCAE, these intensity grades are defined in Table 6.

Table 6. Grading of Adverse Event Severity

Grade	Adjective	Description
Grade 1	Mild	Sign or symptom is present, but it is easily tolerated, is not expected to have a clinically significant effect on the patient's overall health and well being, does not interfere with the patient's usual function, and is not likely to require medical attention
Grade 2	Moderate	Sign or symptom causes interference with usual activity or affects clinical status, and may require medical intervention
Grade 3	Severe	Sign or symptom is incapacitating or significantly affects clinical status and likely requires medical intervention and/or close follow-up
Grade 4	Life-threatening	Sign or symptom results in a potential threat to life
Grade 5	Fatal	Sign or symptom results in death

Note the distinction between the seriousness and the severity of an adverse event. Severe is a measure of intensity; thus, a severe reaction is not necessarily a serious reaction. For example, a headache may be severe in intensity, but would not be classified as serious unless it met one of the criteria for serious events listed in Section 8.1.2.

8.6. Pregnancy of Female Partners

PTC Therapeutics should be notified in the event that a female partner of a patient becomes pregnant at any time after the patient's first dose of study drug. Any such pregnancy occurring on-study or within 60 days of the last administration of study drug must be reported on a

Pregnancy Notification Form (see Study Manual for details). This must be done whether or not an adverse event has occurred and within 24 hours of awareness of the pregnancy. The information submitted should include the anticipated date of birth or pregnancy termination.

Written consent is required prior to collecting and reporting any information on a female partner of a patient.

If possible, the investigator should follow the pregnant female partner of the patient until completion of the pregnancy and notify the PTC Therapeutics medical monitor of the outcome within 5 days or as specified below. The investigator will provide this information as a follow up to the initial Pregnancy Notification Form via the Pregnancy Outcome Form (see Study Manual for details).

If the outcome of the pregnancy meets the criteria for immediate classification as a serious adverse event (ie, spontaneous abortion, stillbirth, neonatal death, or congenital anomaly [including that in an aborted fetus]), the investigator should follow the procedures for reporting serious adverse events, ie, report the event to the PTC Therapeutics Safety Department and follow up by submission of appropriate adverse event CRFs (see Section 8.9).

8.7. Follow-Up of Unresolved Adverse Events

All adverse events should be followed up by the investigator until they are resolved, or the investigator assesses them as chronic or stable. Follow-up of any SAE that is fatal or life-threatening should be provided within one additional calendar week. The investigator should consider protocol guidelines and use his/her discretion in ordering additional tests as necessary to monitor the resolution of such events. In the event of additional investigations, the PTC Therapeutics Safety Department should be informed via e-mail or fax. A patient withdrawn from the study because of an adverse event must be followed by the investigator until clinical recovery is complete and laboratory results have returned to normal, or until progression has been stabilized. Follow-up may need to continue after the patient has discontinued from the study, and additional investigations may be requested by the medical monitoring team.

8.8. Adverse Event Reporting Period

The first day of adverse event reporting will coincide with the day the first dose of study drug is administered. The adverse event reporting period for this study ends with the 6-week (\pm 7 days) Post-Treatment Visit, except as described in Section 8.7. In addition, SAEs occurring in a patient after the study period should be reported to the sponsor if the investigator becomes aware of them.

8.9. Investigator Site Adverse Event Reporting Requirements

Classification of an event as serious or nonserious (see [Section 8.1.2](#)) determines the reporting procedures to be followed. Investigator site reporting requirements for adverse events are summarized in [Table 7](#).

Table 7. Investigator Site Reporting Requirements for Adverse Events

Classification	Reporting Time	Reporting Action
Serious	Within 24 hours	Telephone call, fax, or e-mail to the PTC Therapeutics Safety Department
	Within 24 hours	Fax report or document scan on designated SAE report form to the PTC Therapeutics Safety Department and to site IRB/IEC, as per local IRB/IEC requirements
	Within 5 calendar days	Photocopies or document scan of relevant CRFs (eg, adverse event form, medical history form, concomitant drug/therapy form) and source documents ^a (eg, progress notes, nurses' notes, laboratory and diagnostic test results, discharge summaries) to the PTC Therapeutics Safety Department
	Per CRF submission procedure	Record and submit information on appropriate CRFs
Nonserious	Per CRF submission procedure	Record and submit information on appropriate CRFs

^a Patient name, address, and other personal identifiers should be obscured.

Abbreviations: CRF = case report form, IRB/IEC = Institutional Review Board/Independent Ethics Committee, SAE = Serious Adverse Event

For SAEs, in addition to completing the adverse event portion of the CRF, the SAE report form must also be completed. The SAE report form should be signed by the investigator; however, if the investigator is unable to sign at the time of the event or within 24 hours, the form should be signed by the clinical staff member reporting the SAE (eg, the study coordinator). The SAE report form must be faxed or emailed to the PTC Therapeutics Safety Department and to the site IRB/IEC (if required by local regulations) within 24 hours. Follow up information to the SAE should be clearly documented as “follow up” in the SAE report form and must also be faxed or emailed to the same party. All follow up SAE report forms for the event must be signed by the investigator. Any source documents (eg, progress notes, nurses' notes, laboratory and diagnostic test results, discharge summaries) provided to the sponsor should be redacted so that the patient's name, address, and other personal identity information are obscured. Only the patient's study number and initials are to be provided (in regions where the provision of such information is permitted). The information in the adverse event portion of the CRF and the SAE report form(s) must match or be reconciled. Where the same data are collected, the forms must be completed in a consistent manner. For example, the same adverse event term should be used on both forms.

In the rare event that the investigator does not become aware of the occurrence of an SAE immediately (for example, if a patient initially seeks treatment elsewhere), the investigator is to report the event within 24 hours after learning of it and to document his/her first awareness of the adverse event.

The PTC Therapeutics Safety Department contact information for reporting serious adverse events is provided below. This information is also provided in the Study Manual and in the SAE report form.

PTC Therapeutics Safety Department

Attention: [REDACTED]
Telephone (office): [REDACTED]
Facsimile: [REDACTED]
E-mail: [REDACTED]

